8.3 Adverse Events

The safety and tolerability of subjects will be assessed by the incidence of treatment-emergent adverse events (TEAEs), laboratory test results, vital signs, ECGs, and physical examination findings.

The definitions of an AE or SAE can be found in Appendix 3.

The Investigator will document all AEs in the subject's source document and eCRF. All entries should contain an event term, date of onset, date of resolution, severity, action taken, outcome, relationship to study treatment, and a seriousness assessment.

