8.3.1 Time Period and Frequency for Collecting AE and SAE Information

Any relevant observations made before the end of the Screening and Baseline visit (prior to the first dose of study treatment) are to be recorded on the AE eCRF, but will not be considered TEAEs and will be reported separately from TEAEs. Any relevant observations made after the first dose of study treatment will be recorded as an AE in the subject's AE eCRF (see Section 1.3).

In view of the long half-life of tildrakizumab at doses previously studied, subjects will continue to be monitored throughout the 20-week Observational Safety Follow-up period following the EoT (Week 52) visit. For the purposes of this study, any detrimental change in the subject's condition after the first dose of study treatment and up to the completion of the EoS visit should be considered an AE. For those subjects who may withdraw during the Observational Safety Follow-up period or wash-out period, at least 2 attempts should be made to collect the AEs.

A hospitalization planned by the subject prior to signing the ICF is considered a therapeutic intervention and not the result of a new SAE and should be recorded as medical history. If the planned hospitalization or procedure is executed as planned, the record in the subject's medical history is considered complete. However, if the event/condition worsens during the study, it must be reported as an AE.

Medical occurrences that begin before the start of study treatment but after obtaining informed consent will be recorded on the AE section of the eCRF however will not be considered as TEAEs.

All SAEs will be recorded and reported to the CRO within 24 hours, as indicated in Appendix 3. The Investigator will submit any updated SAE data to the CRO within 24 hours of it being available. The Investigator is responsible for informing the Ethics Committee of the SAE as per local requirements. All AEs/SAEs have to be reported to the Sponsor, whether or not considered causally related to the study treatment or to the study procedures.

Investigators are not obligated to actively seek AE or SAE after conclusion of the study participation. However, if the Investigator learns of any SAE, including death, at any time after a subject has been discharged from the study, and he/she considers the event to be reasonably related to the study treatment or study participation, the Investigator must promptly notify the CRO.

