Tuberculosis (TB) Screening ^a	QuantiFERON® test	

NOTES:

- ^a Only during Screening
- The results of each test must be entered into the electronic case report form (eCRF). The date and exact time of sample collection must be recorded.
- Blood samples are to be collected (prior to study treatment administration), after an electrocardiogram (ECG) and vital sign measurements. At visits where lipids are to be assessed, the blood samples are to be collected (prior to study treatment administration) after 12 hours fasting, following ECG and vital sign measurements.

Appendix 3: Adverse Events: Definitions and Procedures for Recording, Evaluating, Follow-up, and Reporting

Definition of AE

An AE is any untoward medical occurrence in a patient or subject, temporally associated with the use of study treatment, whether or not considered related to the study treatment.

NOTE: An AE can therefore be any unfavorable and unintended sign (including an abnormal laboratory finding), symptom, or disease (new or exacerbated) temporally associated with the use of study treatment.

Events Meeting the AE Definition

- Any abnormal laboratory test results (hematology, clinical chemistry, or urinalysis) or
 other safety assessments (e.g., ECG, radiological scans, vital signs measurements),
 including those that worsen from Baseline, considered clinically significant in the
 medical and scientific judgment of the Investigator (ie, not related to progression of
 underlying disease).
- Exacerbation of a chronic or intermittent pre-existing condition including either an increase in frequency and/or severity of the condition.
- New conditions detected or diagnosed after study treatment administration even though it may have been present before the start of the study.
- Signs, symptoms, or the clinical sequelae of a suspected drug-drug interaction.
- Signs, symptoms, or the clinical sequelae of a suspected overdose of either study treatment or a concomitant medication. Overdose per se will not be reported as an AE/SAE unless it is an intentional overdose taken with possible suicidal/self-harming intent. Such overdoses should be reported regardless of sequelae.

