- "Lack of efficacy" or "failure of expected pharmacological action" per se will not be reported as an AE or SAE. Such instances will be captured in the efficacy assessments. However, the signs, symptoms, and/or clinical sequelae resulting from lack of efficacy will be reported as AE or SAE if they fulfill the definition of an AE or SAE.

Events NOT Meeting the AE Definition

- Any clinically significant abnormal laboratory findings or other abnormal safety assessments which are associated with the underlying disease, unless judged by the Investigator to be more severe than expected for the subject's condition.
- The disease/disorder being studied or expected progression, signs, or symptoms of the disease/disorder being studied, unless more severe than expected for the subject's condition.
- Medical or surgical procedure (e.g., endoscopy, appendectomy): the condition that leads to the procedure is the AE.

- Situations in which an untoward medical occurrence did not occur (social and/or convenience admission to a hospital).
- Anticipated day-to-day fluctuations of pre-existing disease(s) or condition(s) present or detected at the start of the study that do not worsen.
- Pregnancy itself is not regarded as an AE unless there is suspicion that the study treatment may have interfered with the effectiveness of a contraceptive medication. If a pregnancy is reported for a subject, no further study treatment will be administered to this subject and the outcome of all pregnancies (spontaneous miscarriage, elective termination, normal birth or congenital abnormality) must be followed up and documented. Follow-up should be performed up to delivery and examination of the newborn, after which a follow-up report should be sent with any new information regarding the pregnancy and the outcome of the birth.
- All congenital abnormalities/birth defects should be classified as SAEs. Spontaneous
 miscarriages should also be reported and handled as SAEs. Elective abortions without
 complications should not be handled as SAEs but should be reported as a follow-up
 report for the pregnancy. All outcomes of pregnancy must be reported to the Sponsor on a
 Pregnancy Outcomes Report Form.
- Pregnancy outcomes must be collected for the female partners of any males who took study treatment in this study. Consent to report information regarding these pregnancy outcomes should be obtained from the female partner.

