| Effective Date: 10-AUG-2020 | Page 41 of 61 |
|-----------------------------|---------------|

Non-TEAEs will be listed only and will not be included for analysis and summarization.

All AEs will be presented in a by-treatment and by-subject listing for Part 1, detailing the verbatim term, SOC, PT, injection site reaction or not, related to study indication or not, start date, stop date, time since most recent dose of IP, severity, outcome, relationship to study drug, action taken regarding study drug, other action taken, seriousness and criteria for seriousness. Serious AEs (SAEs) and TEAEs leading to study medication discontinuation, AEs of Special Interest (AESI), and events of clinical interest (ECI) will also be presented in separate listings.

An AE profile for the SAF will be provided for Part 1, Parts 2 and 3, and overall, which summarizes the subject incidence, by treatment received for the following information:

- Any TEAEs;
- Drug-related TEAEs;
- Any TEAEs with an outcome of death;
- Treatment-emergent SAEs;
- Drug-related treatment-emergent SAEs;
- TEAEs leading to discontinuation of study medication;
- Drug-related TEAEs leading to discontinuation of study medication;
- Any AEs of special interest, including:
 - Injection site reactions
 - Severe infections
 - o Malignancies (excluding carcinoma in situ of the cervix).
 - Non-melanoma skin cancer
 - Melanoma skin cancer
 - Major Adverse Cardiovascular Events (MACE)
 - Study treatment-related hypersensitivity reactions (e.g., anaphylaxis, urticaria, angioedema, etc.).

| Effective Date: 10-AUG-2020 | Page 42 of 61 |
|-----------------------------|---------------|

Study treatment-related hypersensitivity reactions will be identified based on Sponsor review of treatment-blinded listings of AE preferred terms prior to declaration of the IA DB freeze.

The number and percentage of subjects with TEAEs will be summarized for each treatment arm and/or in total by SOC and PT. Drug-related TEAEs, TEAEs leading to discontinuation of study drug, drug-related TEAEs leading to discontinuation of study drug, treatment-emergent SAEs, and drug-related treatment-emergent SAEs, AESI and ECI will be summarized in the same manner. For these summaries, subjects with multiple AEs will be counted only once per SOC and PT.

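### Protocol Section 8.3.1 counts every post-dose deterioration as an AE while Appendix 3 excludes expected psoriasis progression, so aggregate Part 1 TEAE rows may mix lack of efficacy into the safety comparison

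*Protocol*

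**What the plan says.** Protocol Section 8.3 sends the reader elsewhere for the definition: "The definitions of an AE or SAE can be found in Appendix 3". Section 8.3.1, on when events are collected, then gives its own rule: "For the purposes of this study, any detrimental change in the subject's condition after the first dose of study treatment", through to the end-of-study visit, counts as an AE. That sentence has no exception for psoriasis.

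Appendix 3 has two lists. Among events that are AEs it puts "Exacerbation of a chronic or intermittent pre-existing condition including either an increase in frequency and/or severity of the condition". Among events that are not, it puts "The disease/disorder being studied or expected progression, signs, or symptoms of the disease/disorder being studied, unless more severe than expected for the subject's condition". It also says that lack of efficacy in itself is not reported as an AE or SAE: "Such instances will be captured in the efficacy assessments". Signs and symptoms that result from lack of efficacy still count if they meet the AE definition.

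SAP Section 10.1 defines a TEAE as an AE that starts or worsens after the first dose, with no exclusion for the study disease. It tabulates by treatment, for Part 1 and later parts, any TEAE, TEAEs by maximum severity and TEAEs leading to discontinuation, among others. Its AE listing carries the fields "injection site reaction or not, related to study indication or not". The available text uses the second field in no summary table.

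**The concern.** One psoriasis flare of an expected kind is an AE under one section and not under another. Up to about 35 centers may settle this differently, and no sentence says which text prevails.

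The inconsistency may not be neutral between arms. In Part 1 half the subjects receive placebo for 28 weeks, topical corticosteroids are barred (Sections 6.5.2 and 6.8), and rescue medicine is marked not applicable (Section 6.5.1). If worsening is commoner on placebo and some sites record it as a TEAE, a safety row partly measures efficacy. The rows exposed are those that pool all events: any TEAE, maximum severity and TEAEs leading to discontinuation. SAE status is touched as well, because Appendix 3 says that an event outside the AE definition cannot be an SAE.

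**Working it through.** **1. The two texts side by side**

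| Event after first dose | Section 8.3.1 as written | Appendix 3 |
|---|---|---|
| Psoriasis worsening within expectation | AE | Not an AE |
| Psoriasis worsening beyond expectation for the subject | AE | Study-disease exclusion does not apply; can be an AE |
| No response, no deterioration | Not reached | Not an AE; efficacy data |
| Worsening of another chronic condition | AE | AE |

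Only the first row is in dispute.

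**2. Route into the tables.** Neither Protocol Section 9.4.2.1 nor SAP Section 10.1 removes study-disease events from the TEAE count, so a disputed event that is recorded is tabulated by arm.

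**3. Route into the discontinuation row.** Section 7.1 lists meeting the s-PGA worsening criterion at Week 16 or 28 as a reason to stop treatment, and the protocol does not say whether meeting it is an AE. This route is narrow. The scale ends at 5, entry requires at least 3, and the criterion is a rise of at least 2, so only a subject who enters at exactly 3 can meet it (3 + 2 = 5).

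**4. Direction.** The documents give no worsening rates. Section 4.3 reports Week 16 PASI 75 of 66% on 100 mg against 4% on placebo in the Phase 2 dose-ranging study. That concerns improvement, so it supports more worsening on placebo only indirectly.

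**5. Size, by illustration.** The only plan figure used is 48 per arm. It reproduces: a pooled Z-test for 35% vs 10% gives 43 per arm (80.4% power), and 43 / (1 − 0.10) = 47.8, rounded up to 48. One subject is 1/48 = 2.1 points.

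Assumptions, none from the documents:
- b is the share with some other TEAE, equal in both arms, taken as 30% to 60%.
- w is the share with disputed worsening recorded as a TEAE, taken as 5% to 30% on placebo and 0% to 5% on tildrakizumab.
- The two are independent.

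Any-TEAE = 1 − (1 − b)(1 − w), so tildrakizumab minus placebo = −(1 − b)(w_placebo − w_tildrakizumab).

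| b | w placebo / tildrakizumab | Any-TEAE placebo / tildrakizumab | Difference (points) |
|---|---|---|---|
| 60% | 5% / 0% | 62.0% / 60.0% | −2.0 |
| 50% | 10% / 2% | 55.0% / 51.0% | −4.0 |
| 50% | 20% / 5% | 60.0% / 52.5% | −7.5 |
| 30% | 30% / 5% | 51.0% / 33.5% | −17.5 |

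With disputed worsening left out, every difference is 0. The gap is proportional to the difference in w. If half as many disputed events are recorded in each arm, the −4.0 becomes 0.5 × (5% − 1%) = 2.0 points in the same direction.

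**6. With a real excess.** Suppose other TEAEs occur in 30% on placebo and 35% on tildrakizumab, a true +5 points.
- w of 5% / 0%: 33.5% vs 35.0%, or +1.5.
- w of 10% / 2%: 37.0% vs 36.3%, or −0.7.
- w of 20% / 5%: 44.0% vs 38.25%, or −5.75.

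In the aggregate row a modest excess could be reduced or reversed.

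**The case against.** The strongest reply is that the protocol already shows which text governs. Section 8.3 points to Appendix 3 for definitions, and Section 8.3.1 ends by sending recording and evaluation there. The broad sentence sits under a heading about time period, in a paragraph about the 20-week follow-up, and can be read as setting only when events are collected. This makes Appendix 3 the better reading. It does not settle the matter, because the sentence is worded as a rule for this study and nothing says Appendix 3 overrides it.

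A reader might infer that Appendix 3 also contradicts itself, since psoriasis is a chronic pre-existing condition. The more natural reading is that the exacerbation entry is the general rule and the study-disease entry its exception. A cross-reference would help, but the main conflict is between 8.3.1 and Appendix 3. A reader might also infer that Appendix 3 shuts out all psoriasis worsening. It does not: worsening beyond expectation can be an AE under both texts.

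The reply is also right about visibility. SOC/PT tables by arm would give psoriasis terms their own rows, and at the SAP's 1% threshold for common TEAEs one subject of 48 suffices. Severe infections, malignancies, MACE, hypersensitivity and injection site reactions are summarised separately. Safety is descriptive (SAP Section 3.5), so no test, alpha or power is affected.

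Finally, washout is completed before randomization and active disease is required at Screening and Baseline, so washout alone is weak evidence of later worsening on placebo. The SAP's contents name a list of tables in Section 16 whose text is not available, so it cannot be said that no planned table uses the study-indication field.

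**Conclusion.** The conflict is real and worth correcting. Expected psoriasis worsening is an AE under Section 8.3.1 as written and not under Appendix 3, and whatever sites record goes into the Part 1 TEAE tables. The aggregate rows may therefore mix lack of efficacy into a descriptive safety comparison, plausibly in favour of tildrakizumab.

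The size is unknown. The 2.0 to 17.5 points rest wholly on assumed background and worsening rates and on independence, and they shrink in proportion if fewer disputed events are recorded. The direction is also an inference, and it applies mainly to Part 1, because placebo subjects switch to tildrakizumab at Week 28.

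A reader might conclude that the plan will make tildrakizumab look safer, or will hide an excess of other events. The documents do not support that: they give no rate of recorded worsening, and the SOC/PT rows and AESI categories would still show other events largely undistorted.

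**What to change.** - **Protocol Section 8.3.1:** limit the sentence to a detrimental change *that meets the Appendix 3 definition of an AE*.
- **Protocol Appendix 3:** make the exacerbation entry subject to the study-disease entry in the list of non-AEs, keeping that entry's exception for worsening beyond expectation. Removing the study disease from the exacerbation entry outright would clash with that exception.
- **SAP Section 10.1:** keep all full TEAE tables. Add Part 1 summaries of any TEAE, maximum severity and TEAEs leading to discontinuation without events flagged as related to the study indication, unless Section 16 already has them. State how the flag is set, since Protocol Section 8.3 does not name it among the AE entries.

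The cost is a wording amendment, with ethics committee and, where applicable, regulatory approval (Appendix 1), plus a few filtered tables. The amendment does not harmonise events already recorded, and the filter cannot recover events that sites left out. The filtered tables also drop some flagged events that Appendix 3 properly counts as AEs, so they should be supplementary only.

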8.3.2 Method of Detecting AEs and SAEs

Care will be taken not to introduce bias when detecting AEs and/or SAEs. Open-ended and non-leading verbal questioning of the subject is the preferred method to inquire about AE occurrences.

8.3.3 Follow-up of AEs and SAEs

After the initial AE/SAE report, the Investigator is required to proactively follow each subject at subsequent visits/contacts. Subjects who are discontinued from treatment because of SAEs, and non-serious AEs of special interest (AESI) (as defined in Section 8.3.6), will be followed until resolution, stabilization, the event is otherwise explained, or the subject is lost to follow-up (as defined in Section 7.3). Further information on follow-up procedures is given in Appendix 3.

8.3.4 Regulatory Reporting Requirements for SAEs

All SAEs must be reported according to ICH GCP or local regulations, applying the regulation with the stricter requirements. The report will contain as much available information concerning the SAE to enable the Sponsor's designated pharmacovigilance personnel/CRO to file a report which satisfies regulatory reporting requirements. The SAE report will be notified by Investigator within 24 hours of his/her awareness to the Sponsor's designated pharmacovigilance personnel/CRO. These timelines apply to initial reports of SAEs and to all follow-up reports. All SAEs will be recorded on the SAE report form in the eCRF and source documents.

The following minimum information must be included in the SAE form:

- Name, address and telephone number of the reporting Investigator,
- Study treatment details,
- Subject identification number, initials, gender, and date of birth,
- Description of the SAE, measures taken, and outcome.

Relevant pages from the eCRF may be provided in parallel (e.g., medical history, concomitant drugs). Additional documents may be provided by the Investigator, if available (e.g., laboratory results, hospital report, autopsy report).

The Investigator must respond to any request for follow-up information (e.g., additional information, outcome, final evaluation, other records where needed) or to any question, the Sponsor's designated pharmacovigilance personnel/CRO may have on the SAE. This is necessary to ensure prompt assessment of the event by the Sponsor's designated pharmacovigilance personnel to allow the Sponsor to meet strict regulatory timelines associated with expedited safety reporting obligations.

8.3.5 Pregnancy

Pregnancy itself is not regarded as an AE unless there is a suspicion that the study treatment may have interfered with the effectiveness of the contraceptive medication. If a pregnancy is reported for a subject, no further study treatment will be administered to this subject, and the outcome of all pregnancies (spontaneous miscarriage, elective termination, normal birth or congenital abnormality) must be followed up and documented. Follow-up should be performed up to delivery and examination of the newborn, after which a follow-up report should be sent with any new information regarding the pregnancy and the outcome of the birth.

The pregnancy shall be followed every 3 months during pregnancy until its outcome and 1 month post-delivery. If there are abnormalities present at delivery, the newborn will be followed for an appropriate period, or up to 3 months, to assess the functional and health status of the child.

All congenital abnormalities/birth defects should be classified as SAEs. Spontaneous miscarriages should also be reported and handled as SAEs. Elective abortions without complications should not be handled as SAEs but should be reported as a follow-up report for the pregnancy. All outcomes of pregnancy must be reported to the Sponsor on a Pregnancy Outcomes Report Form.

Pregnancy outcomes must be collected for the female partners of any males who took study treatment in this study. Consent to report information regarding these pregnancy outcomes should be obtained from the female partner.

Pregnancies must be reported to IQVIA Clinical Pharmacovigilance and Safety Services using the reporting details provided in Appendix 3 within 24 hours of becoming aware of the pregnancy.

8.3.6 Adverse Events of Special Interest

Injection site reactions, including injection site urticaria, pruritus, pain, reaction, erythema, inflammation, edema, swelling, bruising, hematoma, and hemorrhage, can be observed with the use of tildrakizumab. In general, these AE are well-tolerated and tend to disappear spontaneously, but if any of those occur in this study, they will be captured as AEs of special interest.

The events of severe infections, malignancies (including non-melanoma and melanoma skin cancer), major adverse cardiovascular events (MACE)s, and study treatment-related hypersensitivity reactions (see Appendix 3) will be identified as AESIs for summarizing in this study. Major Adverse Cardiovascular Events include non-fatal stroke, non-fatal myocardial infarction, and cardiovascular death. An AESI must be reported to the sponsor as if it were an SAE.

